1.0.2 Study Outcomes

1. The primary lipid and lipoprotein endpoints will be plasma concentrations of total cholesterol and triglycerides, low density lipoprotein cholesterol, low density lipoprotein size, high density lipoprotein cholesterol, and apoproteins B and A-I.
2. A second group of lipid and lipoprotein endpoints will include apo E genotypes, HDL subfractions lipoprotein (a) and very low density lipoprotein cholesterol.
3. The primary hemostatic endpoints will be factor VII and plasminogen activator inhibitor I, and beta thromboglobulin.
4. A second group of hemostatic factors may include fibrinogen and platelet aggregation by flow cytometry.
5. Fasting plasma insulin and glucose levels will also be primary endpoints.
6. Other secondary endpoints will include postprandial lipids, lipoproteins, insulin, and glucose levels.
7. Several ancillary studies may be carried out to test sub-hypotheses.

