1. Blood Collection Tray.

Blood collection trays are prepared in advance for the following day. Each tray is stocked with a full supply of blood-drawing equipment for three to four participants and holds individual blood collection racks for each participant in an ice bath. Several racks are prepared to hold various plastic tubes and vials for the final serum and plasma aliquots. The blood collection tube rack and aliquot tube rack are pre-labeled with the appropriate code numbers for the participants drawn that day.

2. Blood Collection Rack.

The collection tray itself is made of hard plastic which is unbreakable and can be easily cleaned. The tray has 10 individual compartments which will be filled with the following supplies:

- 21 g butterfly needles with luer adapter
- alcohol swabs
- Band-Aids
- Gauze
- Tourniquets (2)
- Vacutainer holders
- Needle/Sharps container
- Smelling salts
- Timer/Stop watch
- Scissors
- Adhesive tape
- Styrofoam ice bath filled approximately
10 minutes before draw
- Pencils/Pens
- Latex gloves
- Test tube racks (2)

A separate rack contains the necessary draw tubes, etc. for each participant. The tubes are arranged according to the priority of the draw. This rack will fit into the blood collection tray. The blood collection tubes are pre-labeled with identification numbers.

3. Description of blood collection tubes for endpoint package.

Tubes 1 and 6 are a 10 ml siliconized yellow/black stopper tube. This tube contains thrombin so that the blood clots to form serum in 5 minutes. Aliquots are coded red. This serum is used for the lipid profiles, glucose, insulin, and apoproteins.

Tube 2 is a 4.5 ml blue-top tube containing 0.5 ml of 3.8% sodium citrate. It is crucial that this tube remain at room temperature. After centrifugation, plasma is aliquoted into green-coded aliquots. The plasma will be used for Factor VII coagulation assay. This tube will be used to provide seven 3-uL aliquots for platelet activation in week 7.

Tube 3 is also a 4.5 ml blue-stopper tube identical to Tube 3. It is different in the way it is processed. Instead of room temperature, this tube must be placed on ice after filling. Plasma from this tube is aliquoted into blue-coated aliquots and will be used for fibrinogen assay and PAI-1 assay.

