Processing should be done immediately following venipuncture. Personal protective equipment (non-permeable lab coats, double gloves with at least one Latex pair, spatter shield) must be worn. Flowchart is included at the end of this section to diagram this process (Figure 2).

B. Immediate Processing of Endpoint Samples:

Upon reaching the blood processing station, remove the blood tube drawing rack and ice bath containing tubes from the blood collection tray. The rack should contain three tubes: #1, #2, #6. The ice bath should contain three tubes: #3, #4, #5. All tubes should be processed within 30 minutes of phlebotomy. The corresponding aliquot racks (two per patient) should be ready. Rack #1 (with color codes blue, clear and purple) should be placed in an ice bath. Rack #2 (with color codes red and green) remains at room temperature.

C. Centrifugation:

Tubes #3, #4, and #5 are centrifuged at 4°C for 10-20 minutes at 3,000 g. The centrifuge may need to be precooled to 4°C. 4.5 ml, 5 ml, and 7 ml balance tubes are required for tubes #3, #4 and #5. Simultaneously, tubes #1, #2 and #6 are centrifuged at room temperature for 10-20 minutes at 3,000 g. A 4.5-ml balance tube may be required for tube #2. Once centrifuged, the maximum time allowed before aliquoting is 10 minutes. While these tubes are spinning, the blood collection tray can be restocked with tube rack and blood collection tubes, ice, and forms for the next participant. Recheck labels on the two aliquot racks. Perform any necessary clean-up.

D. Aliquots:

Allow the centrifuge(s) to come to a complete stop. Remove tubes from the refrigerated centrifuge and place in an ice bath, being careful not to shake the tubes. Remove tubes from the room temperature centrifuge. Place in tube rack at room temperature. Assess the plasma. Mark o. the Phlebotomy Processing Form if lipemic (L), icteric (I), hemolyzed (H), clotted (C). Follow the

outline on the Phlebotomy Processing Form for aliquoting the samples. Checkmark on the form if the aliquot is completed, and mark any different volumes. Be careful not to disturb the other white cell layers. If plasma is a lower than expected volume, use one less aliquot rather than disturb the red cells or buffy coat. Do not have any red cells in the aliquots. Use a new pipette tip for each tube type. Recap aliquots after each draw tube has been pipetted.

		ALIUQUOT
Tube #5	Use 500 uL MLA Cryovials (6) - 0.5 mL plasma/cryovial	Rack 1 (on ice) Lavender code

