Once centrifuged, maximum time before aliquoting is 20 minutes; after aliquoting all samples, freeze within 30 minutes.

IV. URINE COLLECTION

Urine samples will be collected the mornings of two scheduled blood draws per diet period (weeks 6,7). Participants should be provided a plastic bottle (labeled with the subject ID number) the day before with instructions (See Appendix II) to collect the first urine sample when they get up the next morning. This sample should be brought to the lab when they arrive for the drawing of their blood sample. Note the receipt of the sample on the Urine Collection Form (Appendix II).

Before aliquoting, mix the sample by swirling the bottle. Remove the cap. Aliquot 2 ml in each of five 2-ml cryovials pre-labeled with the subject ID. Place yellow caps on these samples and freeze at -80°C .

V. POSTPRANDIAL BLOOD COLLECTION AND PROCESSING

The processing of samples for the postprandial studies is summarized in Table 6.

A. Regular diet

When the subject returns before lunch and before dinner, one 7-ml red top tube is drawn. This tube should sit at room temperature for at least 45 minutes to allow the blood to clot. The tube is then centrifuged for 30 minutes at 4°C at 3000xg.

Four 0.5 ml aliquots of serum are placed into four cryovials labeled with the subject ID and coded for the appropriate time point for this postprandial study. Each vial is capped with a red cap and frozen at -80°C .

B. Fat load

Each subject will return at 4 and 8 hours after consuming the fat load. Two tubes of blood are drawn at each time - a 7-ml red top tube (serum) and a 7-ml purple top tube (EDTA plasma) and a 4.5-ml blue top (citrate plasma). The purple top tube must be protected from light to prevent degradation of these compounds; if they will not be processed immediately, they should be wrapped in foil.

Red top tube

The red top tube should be allowed to sit at room temperature for 45 minutes to clot. The tube is then centrifuged for 30 minutes at 4°C at 3000xg.

Four 0.5 ml aliquots of serum are placed into four cryovials labeled with the subject ID, and coded for the appropriate time point for this postprandial study. Each vial is capped with a red cap and frozen at -80°C.

Purple top tube

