APPENDIX IV

APPENDIX IV: DETAILED PROTOCOL FOR BLOOD COLLECTION

A. Preparation for Specimen Collection:

Preparation for specimen collection is done in the following manner:

Early morning, prior to arrival of any participants:

- 1) Check to make sure that blood collection tray is properly equipped. Every item on the checklist must be ready before proceeding.
- 2) Check that each vacutainer tube is properly labeled with the appropriate participant number and number 1-4 (baseline) or 1-5 (endpoint) in order of draw. A sheet of numbered labels will be provided for each participant.
- 3) Check that the sample processing station is properly equipped. Every item on the checklist must be ready and in its proper position.
- 4) Check that each sample aliquot tube is labeled with its appropriate participant identification number and in its proper rack.
- 5) Check that the participant Phlebotomy Processing Forms are labeled and included with the blood collection tray.
- 6) Perform quality control check on refrigerator temperature (refrigerator temperature log).
- 7) Perform quality control check on freezer temperature (freezer temperature log).
- 8) Make sure the phlebotomy area is tidy and stocked with extra smelling salts, basin, disposable wash clothes, and that the blood mixer is functional.

Approximately 10 minutes before scheduled participant arrival:

- 1) Fill styrofoam bath 3/4 full with crushed ice.

At participant arrival:

- 1) Check that the ID number on the tubes matches the participant ID.

B. Venipuncture

- 1. Precautions for handling blood specimens:**

In accordance with OSHA regulations on blood borne pathogens (see appendix for the complete OSHA regulations), the following laboratory safety protocol for field-center laboratories is recommended: Use of non-permeable lab coats, Latex gloves, and face shields when handling any blood in any situation where splashes, spray, splatter, or droplets of blood may be generated and eye, nose, mouth contamination can be reasonably anticipated. Follow universal precautions when handling any blood products. Contaminated needles and sharps shall be immediately placed in a puncture-resistant, leak-proof container. Never re-cap or break needles. Hepatitis B vaccine should be offered to all technicians handling blood.

- 2. Phlebotomy area:**

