- h) Make sure the participant's arms are in a flat or dominant position while maintaining the tube below the site when the needle is in the vein. It might be helpful to have the participant make a fist with the opposite hand and place it under the elbow for support.

- i) Grasp the sheath of the needle holder and push the tube forward until the butt end of the needle punctures the stopper, exposing the full length of the needle.
- j) Note the blood flow into the first collection tube. If blood is flowing freely, the butterfly needle can be taped to the participant's arm for the duration of the study. If the blood flow is very slow, the needle may not be positioned correctly.
- k) Remove the tourniquet at two minutes. Note the time on the PP form. Once the draw has started, do not change the position of the tube until it is withdrawn from the needle. If blood flow ceases after the tourniquet is removed, it may be reapplied for another two minutes, but this is noted on the Phlebotomy Processing Form.
- l) Keep a constant, slight amount of pressure (in the direction of the needle) on the end of the tube (especially tubes #1 and #2). This prevents release of the shut-off valve and stopping of blood flow, do not bring pressure or reintroduce pressure after completion of the draw.
- m) Fill each vacutainer tube as completely as possible; i.e., until the vacuum is exhausted and the blood flow ceases. If a vacutainer tube fills only partially, remove the vacutainer and attach another without removing the needle from the vein. As each tube is filled, mix by gently inverting before placing tube on the mixer. (See Section Blood Mixing During Venipuncture.)
- n) When the blood flow ceases, remove the tube from the holder. Shut off valve recovers the point, stopping blood flow until the next tube is inserted (if necessary).
- o) Average venipuncture time is 3-6 minutes, but any difficulties may increase this time to 10 or 15 minutes.

7. Removing the Needle:

To remove the needle, lightly place clean gauze over the venipuncture site. Remove the needle quickly and immediately apply pressure to the site with a gauze pad. Discard needle into puncture-proof sharps container. Have the participant hold the gauze pad firmly for 2 minutes to prevent a hematoma. Remove tube from the blood mixer and place on ice (#4,#5) and at room temperature (#1,2,3).

8. Bandaging the Arm:

a) Under Normal Conditions:

- 1) Set the gauze pad down over the site, continuing mild pressure.

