- 2) Apply an adhesive or gauze bandage over the veni puncture site after making sure that blood flow is stopped.
- 3) Tell the patient to leave the bandage on for at least 15 minutes.

b) If the patient continues to bleed:

- 1) Apply pressure on the site with a gauze pad. Keep the arm elevated until the bleeding stops.
- 2) Wrap a gauze bandage tightly around the arm over the pad.
- 3) Tell the patient to leave the bandage on for at least 15 minutes.

9. Procedures for difficult draw and complications of blood drawing.

If a blood sample is not forthcoming, the following manipulations may be helpful.

- a) If there is a sucking sound, turn the needle slightly or lift the holder in an effort to move the bevel away from the wall of the vein.
- b) If no blood appears, move needle slightly in hope of entering vein. Do not probe. If not successful, release tourniquet and remove needle. A second attempt can be made on the other arm.
- c) Loosen the tourniquet. It may have been applied too tightly, thereby stopping the blood flow. Apply the tourniquet loosely. If the tourniquet is the Velcro type, quickly release and press back together. Be sure, however, that the tourniquet remains on for no longer than 2 minutes at a time.

- d) The phlebotomist should not attempt to venipuncture more than twice.
- e) Reassure the participant that the inability to obtain a clean venipuncture is not any sign of a medical problem on his/her part.
- f) If venipuncture is unsuccessful, the participant must be rescheduled at a later date with a different field center phlebotomist.

10. Syringe Technique for Venipuncture

Collection of blood sample using syringes may also be used if the phlebotomist, upon examination of the participant's veins, feels that sample will be difficult to obtain by vacutainer method. Blood collection using syringes should be used only if the phlebotomist anticipates a difficult draw (vein collapse, small veins, etc.).

11. Blood Mixing During Venipuncture:

Each tube should be treated as follows:

- a) Serum (#1,6) - Invert once, place on rack at room temperature.
- b) Citrate (#2) on mixer for 30 seconds then place on rack at room temperature.
- c) Citrate (#3) on mixer for 30 seconds then place in ice bath.
- d) Diatube (#4) on mixer for 30 seconds then place in ice bath.
- d) EDTA (#5) on mixer for 30 seconds then place in ice.

12) Precautions:

- a) When a participant feels faint or looks faint following the blood drawing:

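### Chapter 8, Appendix IV, step B.7 sends Tube 3, the source of the primary endpoint PAI-1, to room temperature, while every other instruction in the chapter keeps it on ice or at 4°C

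*Protocol*

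**What the plan says.** Section 1.0.2 of the protocol states: "The primary hemostatic endpoints will be factor VII and plasminogen activator inhibitor I, and beta thromboglobulin". Chapter 8, II.B.3 describes Tubes 2 and 3 as the same 4.5 ml citrate tube. Tube 2 must stay at room temperature for factor VII. Of Tube 3 it says: "Instead of room temperature, this tube must be placed on ice after filling", and its plasma "will be used for fibrinogen assay and PAI-1 assay".

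At the processing station, III.B says: "The ice bath should contain three tubes: #3, #4, #5". In Appendix IV, B.11 (blood mixing) says: "Citrate (#3) on mixer for 30 seconds then place in ice bath".

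Appendix IV, B.7 (removing the needle) instead tells staff to take tubes off the mixer and "place on ice (#4,#5) and at room temperature (#1,2,3". It gives no place for Tube 6.

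Two neighbouring instructions also conflict with the rest of the chapter. Appendix IV, A.2 has tubes labelled with "number 1-4 (baseline) or 1-5 (endpoint) in order of draw", although the endpoint package has six tubes. On timing, III.H says: "Once centrifuged, maximum time before aliquoting is 20 minutes; after aliquoting all samples, freeze within 30 minutes". III.C allows 10 minutes from centrifugation to aliquoting, and III.E allows 10 minutes to freezing.

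**The concern.** Temperature is what the manual uses to distinguish Tube 3 from Tube 2. A bedside step that puts Tube 3 in the room-temperature group orders, for a primary-endpoint sample, the condition the manual excludes for that tube. Staff who follow B.7 and staff who follow II.B.3 or B.11 would handle the same sample differently, and both could say they had kept to the protocol.

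The discrepancy would be hard to find afterwards. Under Table 7 the endpoint samples are shipped to the laboratories only at the end of Period 3, so assay results give no warning during feeding. The Phlebotomy Processing Form, as shown, has no entry for the temperature at which a filled blood tube was held. A technician who obeyed B.7 would also have no deviation to report. Chapter 8 itself warns in its introduction that wrongly drawn or processed blood may give imprecise or invalid results.

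**Working it through.** There is no plan figure to reproduce. The check is a comparison of every instruction on Tube 3, a check of how many tubes the package has, and a count of draws.

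**Step 1. Instructions on Tube 3, side by side**

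| Place in Chapter 8 | Tube 3 |
|---|---|
| II.B.3, tube description | on ice after filling |
| II.B.4, priority of tubes | kept on ice |
| III.B, arrival at processing | in the ice bath |
| III.C, centrifugation | spun at 4°C |
| III.H, time limits (third entry, citrate) | 4°C, 30 minutes |
| Appendix IV, B.11 | ice bath after 30 seconds on the mixer |
| Appendix IV, B.7 | room temperature |

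Six instructions keep the tube cold and one does not. No sentence ranks the appendix above or below the main text, and the appendix disagrees with itself.

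**Step 2. Tube 6**

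II.B.4, III.B, III.C and B.11 all place Tube 6 at room temperature. B.7 does not list it.

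**Step 3. Size of the tube set**

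II.A and Table 1 give about 41 ml per endpoint draw. The tubes in II.B.3 are two of 10 ml (1 and 6), two of 4.5 ml (2 and 3), one of 5 ml (4) and one of 7 ml (5):

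2 × 10 + 2 × 4.5 + 5 + 7 = 20 + 9 + 5 + 7 = 41 ml.

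The stated volume needs all six tubes. Tube 4 is drawn only in weeks 5 and 6, so the week 7 set is tubes 1, 2, 3, 5 and 6. Labels 1 to 5 do not fit that week either.

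**Step 4. Number of draws that meet the conflicting text**

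Inputs: PAI-1 and fibrinogen are each tested three times per diet phase, in weeks 5, 6 and 7 (Table 4); there are three feeding periods; the assumed sample is 100 participants (section 2.0, Table 1).

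- Per participant: 3 draws × 3 periods = 9.
- In total: 9 × 100 = 900.

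This is the number of Tube 3 draws with full retention. It is a ceiling on exposure to the contradiction and does not estimate how many samples would be mishandled.

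**Step 5. Time limits**

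- Centrifugation to aliquoting: 10 minutes (III.C) against 20 minutes (III.H).
- Aliquoting to freezing: 10 minutes (III.E) against 30 minutes (III.H).

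**The case against.** The strongest reply is that B.7 would seldom take effect. Step B.6(m) says each tube is mixed as it fills and refers to the blood mixing section, B.11, which moves Tube 3 to the ice bath after 30 seconds on the mixer. Tube 3 is drawn third, and an average venipuncture lasts 3 to 6 minutes, so it should normally be on ice before the needle comes out. B.7 acts on whatever is still on the mixer. Later, III.B states which tubes belong in the ice bath, so a Tube 3 standing in the rack would be visible. Technicians were certified in Protocol 1 and are recertified before each blood-drawing year.

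This stands as far as frequency goes. It does not remove the contradiction: B.7 still names Tube 3 for room temperature. The processing-station check can only catch the error after some warm time has passed. The training video described in section X.B covers Diatube filtering and platelet treatment; Tube 3 handling is not listed.

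A reader might infer more than the documents support:

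- **That some 900 PAI-1 samples are compromised.** That figure counts all planned draws; the number handled under B.7 is unknown.
- **That Tube 3 stands warm for 30 minutes.** The 30 minutes is the manual's maximum time to processing, and for Tube 3 it is stated at 4°C. Reaching it at room temperature would also need the III.B check to fail.
- **That diet contrasts are biased.** Each participant is assigned a diet sequence (5.4.2), and principal investigators, coordinators and laboratory technicians are masked to diet (4.3). Nothing links tube handling to diet. Handling that stays constant within a participant cancels in within-participant comparisons; handling that changes between draws adds noise. The documents give no size or direction for a temperature effect on PAI-1.
- **That B.7 is left over from a five-tube set.** The missing Tube 6 and the 1-to-5 labels make this plausible, but the manual does not say so.
- **That Tubes 2 and 3 are separate only for temperature.** Tube 2 also supplies platelet aliquots in week 7.

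**Conclusion.** The manual is wrong as written. One operative step orders room temperature for the tube that yields PAI-1 and fibrinogen, against six instructions to keep it cold, and nothing resolves the conflict. Up to about 900 draws face it, assuming 100 participants who complete all nine draws. The supported consequence is avoidable pre-analytical variation in a primary hemostatic endpoint and in fibrinogen, within and between centers. Its size cannot be given from the documents, and bias between diets is not demonstrated. The labelling range and the two pairs of time limits are real conflicts of the same kind and should be settled in the same correction.

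**What to change.** 1. Reword Appendix IV, B.7 to agree with B.11 and III.B: tubes 3, 4 and 5 on ice; tubes 1, 2 and 6 at room temperature.
2. Make the endpoint labelling in Appendix IV, A.2 cover tubes 1 to 6.
3. Have the Laboratory Subcommittee settle one limit from centrifugation to aliquoting and one from aliquoting to freezing, and state the same values in III.C, III.E and III.H.
4. Send the corrected page and a short notice to phlebotomists at all four field centers before the next draw.

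The cost is a few lines of text and one memo. No extra blood, equipment or analysis is needed.

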9.1 GENERAL INSTRUCTIONS FOR FILLING OUT FORMS

9.1.1 Background

The Dietary Effects on Lipoprotein and Thrombogenic Activity (DELTA) study will use paper forms to collect most data. Data from these paper forms will then be entered at a later date either into a computer-assisted data management system (DMS) located at each field center and the food analysis laboratory or into non-standard format files at the central lipid and hematology laboratories.

The purpose of this section is to provide instructions for completing these paper forms. It should be read carefully prior to working with any forms. The form-specific instructions should then be read before filling out each form.

9.1.2 Form Structure

Most paper forms in DELTA are similar in design to the forms layout of the computer screens used for data entry. The paper forms are organized by pages, but the forms in the data management system are organized by computer screens. This may cause some problems in locating an item on a paper form and the corresponding item on the computer screen, however, the items are listed in the same order.

The forms are structured with a header of the form title, form code, form version number, and date of form version across the top of each page. The first page begins with the key data fields of participant DELTA ID number and a visit date. The form code, form version number, participant DELTA ID number, and visit date comprise a unique set of data which identify an individual form type for a participant at a certain point in time on the study database.

Following these header and key data items on the forms are the questions for the participants. Instructions to the interviewer are in brackets ("[]") on most forms.

An example of a typical "first page" is presented in Figure 1.

Figure 1: Example of DELTA Form - First Page

Participant Weekly Monitoring

**Form Code: PWM
Version B 5/10/94**

DELTA ID: _____

Monday's DATE: / /
[THIS WEEK] (mm/dd/yy)

1. Code Number of personnel completing this form: _____

BLOOD DRAW

[Complete numbers 2-4 during weeks 5, 6, 7.]

2. Period 1 2 3 [Circle correct number]

3. Week 5 6 7 [Circle correct number]

4. Date of blood draw / /
mm/dd/yy

WEIGHT [THIS week]

[Participants are weighed before dinner, without shoes or coats.]

5. a. Date of first weekly weight: / /
(mm/dd/yy)

First weekly weight, either in lbs or kg:

b. lbs: _____ or c. kg: _____

d. Current calorie level: 1500 2000 2500 3000 3500 [Circle correct number]

6. a. Date of second weekly weight: / /
(mm/dd/yy)

Second weekly weight, either in lbs or kg:

b. lbs: _____ or c. kg: _____

d. Current calorie level: 1500 2000 2500 3000 3500 [Circle correct number]

